4.1 Inclusion Criteria

All participants in the study must meet all of the following inclusion criteria to participate in this study.

- Male or female, between 18-80 years old, diagnosed with chronic rhinosinusitis who have undergone previous functional endoscopic sinus surgery including at minimum maxillary antrostomy and anterior ethmoidectomy
- Active mucopurulence on endoscopic examination with corresponding culture demonstrating pathogenic bacterial growth
- · Completion of written informed consent
- No prior enrollment into this study
- Refractory to maximal medical therapy

4.2 Exclusion Criteria

Candidates meeting any of the following exclusion criteria at baseline will be excluded from study participation.

- Patient has not had prior endoscopic sinus surgery consisting of at minimum bilateral maxillary antrostomy and anterior ethmoidectomy
- Patient is currently being treated with oral antibiotics
- Patient has been treated with oral or topical antibiotics within the past 14 days
- Participation in an investigational drug study simultaneously with participation in this study
- Concurrent use of oral steroids
- Allergy to Tobramycin, Mupirocin, Gentamicin and Levofloxacin
- Known to currently be pregnant

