2 BACKGROUND AND RATIONALE

2.1 Background on Condition, Disease, or Other Primary Study Focus

There is a population of patients who have chronic rhinosinusitis that is refractory to maximal medical therapy including treatment with saline and steroid nasal irrigations as well as with oral steroids and antibiotics.

The evidence for use of topical antibiotics in current literature is conflicting. The few double blind randomized control studies cited have significant limitations including small sample size, variable intervention medications and delivery methods as well as variable outcomes measured¹⁻⁵. Other studies have shown that use of topical antibiotics in CRS has trended toward positive change in symptom score and endoscopic physical exam findings⁶. In addition, topical antibiotics are currently being used commonly at this institution for patients with recalcitrant chronic rhinosinusitis with good clinical anecdotal result. A well designed study is warranted to further investigate the utility of topical antibiotics in chronic rhinosinusitis.

One concern with topical antibiotics limiting widespread use is perceived increased risk of causing antibiotic resistance. Non-standardized dosage patterns has led to the concern that patients are potentially being treated with subtheraputic dosages. Others postulate that treatment with topical antibiotics against susceptible bacteria may have the effect of inducing biofilm production from resistant bacteria⁷. In contrast, advocates for topical antibiotics expect topical delivery to deliver high concentrations of antibiotics to the sinonasal cavity where they may penetrate a bacterial biofilm, and avoid the systemic effects of enteral or parenteral antibiotics⁷. Further study is warranted to further describe the potential association of topical antibiotic treatment of the sinonasal cavity with antibiotic resistance.

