5.3 Concomitant Interventions

5.3.1 Allowed Interventions

Any additional medications prescribed to the patient as part of their ongoing therapy for chronic rhinosinusitis including nasal saline irrigations, steroid irrigations, or topical sprays.

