5.3.3 Prohibited Interventions

Patients will be excluded if they are prescribed concomitant oral steroids

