9.4 Outcomes

9.4.1 Primary Outcome

Post treatment assessment of presence of antibiotic resistant organism as assessed by nasal swab sent for gram stain, culture and sensitivity

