9.5 Data Analyses

Statistical Methods

Continuous patient characters will be summarized with means and standard deviations for features that are approximately normally distributed and with medians, interquartile ranges, and ranges otherwise. Categorical features will be summarized with frequency counts and percentages.

Primary endpoint:

Number and proportion of patients who developed antibiotic resistance organism will be summarized. 95% confidence intervals will be provided for the proportion.

Secondary endpoint:

1) SNOT-22 symptom scores and Lund-Kennedy endoscopic exam score will be summarized as mean (standard deviation) and median (range).

2). Definition of adherence to study intervention will be to complete 25 of 28 days of topical antibiotics and attend the pre-intervention / enrollment visit as well as the post-intervention assessment visit. Number and proportion of patients with adherence will be reported.

3) Audiometric data will be summarized as a mean (standard deviation) and median (range)

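### The antibiotic exclusions in 4.2 do not cover the parenteral route, so resistance selected by a recent parenteral course can enter the primary result

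*Combined protocol and SAP*

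**What the plan says.** Section 4.2 has two antibiotic exclusions, each limited by route. For current use: "Patient is currently being treated with oral antibiotics". For recent use: "Patient has been treated with oral or topical antibiotics within the past 14 days". Current topical use is caught by the second, since it falls within the past 14 days. Parenteral use is caught by neither.

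The protocol is aware of the route. Section 2.1 says that advocates expect topical delivery to "avoid the systemic effects of enteral or parenteral antibiotics".

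The concomitant-treatment rules do not fill the gap. Section 5.3.1 allows "Any additional medications prescribed to the patient as part of their ongoing therapy for chronic rhinosinusitis", and the only prohibition in 5.3.3 is "Patients will be excluded if they are prescribed concomitant oral steroids".

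The primary result is worded in two ways. Section 9.4.1 defines the outcome as "Post treatment assessment of presence of antibiotic resistant organism as assessed by nasal swab sent for gram stain, culture and sensitivity". Section 9.5 plans the analysis as "Number and proportion of patients who developed antibiotic resistance organism will be summarized", and adds that "95% confidence intervals will be provided for the proportion". Neither section states how the post-treatment culture is to be compared with the baseline culture.

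**The concern.** The protocol gives no reason for its washout. The natural one is to keep recent antibiotic pressure from distorting the cultures, and that reason does not depend on how the antibiotic was given. A systemic course shortly before baseline can suppress susceptible strains and favour resistant ones, which may then appear on the post-treatment swab.

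The study asks whether topical therapy is followed by resistant organisms, and it has one arm. No comparison group can show that a resistant organism found afterwards came from an earlier systemic course and not from the study drug. With 20 or 40 patients, a single such case can change the headline from no resistance to some.

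**Working it through.** The plan states no figure on this point, and 9.2 says that no sample size calculation is required, so there is nothing to reproduce. The check has three parts.

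**1. Does any section exclude the patient?** Take a candidate receiving intravenous antibiotics on the day of the baseline swab, or who stopped a few days before.

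| Section | What it covers | Excludes this patient? |
|---|---|---|
| 4.1 | Prior surgery, mucopurulence with pathogenic growth, refractory disease; no antibiotic-free period | No |
| 4.2, current use | Oral | No |
| 4.2, past 14 days | Oral or topical | No |
| 5.3.1 | Permits other medication for the condition | No |
| 5.3.3 | Oral steroids | No |
| 6.2.2 | Medication reconciliation, applied to the written criteria | No |

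The reconciliation could bring the course to light, but no written criterion then acts on it.

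**2. How could resistance from that course reach the primary result?**

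| Resistance selected by the earlier course | 9.4.1: present after treatment | 9.5: developed, read as absent at baseline |
|---|---|---|
| Detected at baseline, persists to the post-treatment swab | Counts | Does not count |
| Missed at baseline, found on the post-treatment swab | Counts | Counts |
| Not found on the post-treatment swab | Does not count | Does not count |

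The baseline reading of 9.5 is an interpretation, because the section does not define the term.

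**3. What does one misattributed case do?** The sample size is 20 in the Précis and section 3, and 40 in 9.1 and 9.2. That conflict is a separate matter, so both are shown. The plan does not name an interval method; exact Clopper-Pearson 95% limits are used here.

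- For 0 of n, the upper limit is 1 − 0.025^(1/n): 16.8% at n = 20 and 8.8% at n = 40.
- For 1 of n, the lower limit is 1 − 0.975^(1/n): 0.13% at n = 20 and 0.06% at n = 40.
- For 1 of n, the upper limit solves (1 − p)^n + n·p·(1 − p)^(n−1) = 0.025: 24.9% at n = 20 and 13.2% at n = 40.

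| n | No case | One case | Change in proportion |
|---|---|---|---|
| 20 | 0% (0 to 16.8%) | 5.0% (0.1 to 24.9%) | 1/20 = 5.0 points |
| 40 | 0% (0 to 8.8%) | 2.5% (0.1 to 13.2%) | 1/40 = 2.5 points |

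The documents do not give the share of enrolled patients with recent parenteral exposure. Taking assumed shares s, the chance of enrolling at least one such patient is 1 − (1 − s)^n:

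| Assumed share | n = 20 | n = 40 |
|---|---|---|
| 1% | 18% | 33% |
| 2% | 33% | 55% |
| 5% | 64% | 87% |
| 10% | 88% | 99% |

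These are chances of enrolling an exposed patient, not of a misattributed resistance event. The latter also needs resistance to be selected by the course and to follow one of the counting paths in part 2, so it can be no larger and may be much smaller.

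**The case against.** The strongest reply is that every patient has a baseline culture with sensitivities (2.2, 3 and 6.1), and that 9.5 counts patients who developed a resistant organism. On the ordinary meaning of that word, resistance already seen at baseline is not counted. This stands. A reader might infer from the gap in 4.2 that resistance from an earlier parenteral course necessarily ends up in the primary result; the documents do not support that. It counts directly only under 9.4.1, and only if it persists. The reply is incomplete, because 9.5 states no baseline rule and a baseline swab can miss a strain.

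Second, nothing shows that these patients receive parenteral antibiotics. Section 2.1 describes refractory patients as having had oral steroids and antibiotics, and mentions the parenteral route only as a general contrast. Participants are outpatients for whom topical therapy has already been chosen (4.3). This stands too. That refractory patients are often escalated to parenteral treatment is tempting to assume, but it would be an inference.

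Third, a reader might count altered baseline sensitivities, and so a different choice of study drug, as a further error. Treatment is meant to follow the organism and sensitivities found at baseline, so a changed choice is not in itself a fault.

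Fourth, 5 or 2.5 points per case is simply 1/n and would apply to any misclassified patient. That is correct. It shows how sensitive the result is, not how often the problem arises.

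Finally, a route-neutral washout leaves untouched any resistance selected by a course that ended more than 14 days earlier, and it does not settle 9.4.1 against 9.5. Both are true. They limit what the change achieves but do not argue against making it.

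**Conclusion.** The gap in eligibility is plain from the text: as written, a patient on or just off parenteral antibiotics may enroll. The effect on the primary result is possible, not certain, and depends on which outcome wording governs. If it occurs, one case adds 5.0 points at n = 20 or 2.5 points at n = 40, and raises the exact upper limit from 16.8% to 24.9% or from 8.8% to 13.2%, assuming no other cases.

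The frequency is unknown and probably small in this outpatient population. In a descriptive pilot this is a minor point, worth correcting because it costs so little. The conclusion assumes that the criteria are applied as written. If the sponsor meant all systemic antibiotics, only the wording is at fault. A parenteral course continuing beyond the baseline swab falls under 5.3.1 and 5.3.3 and is a separate question.

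**What to change.** Replace the two antibiotic bullets in 4.2 with one that does not depend on route, for example: *any antibiotic, by any route (oral, parenteral, inhaled or topical), at the time of the baseline swab or in the 14 days before it.* This keeps the sponsor's own window, ties it to the swab, and removes any doubt about whether an inhaled antibiotic counts as topical. Check it at the medication reconciliation already planned in 6.2.2.

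The cost is one line of protocol text and possibly a few otherwise eligible patients. If exposure is rare, almost none are lost; if it is less rare, the exclusion does more to protect the result.

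Separately, 9.4.1 and 9.5 should be reconciled by stating how the post-treatment culture is compared with baseline, since that decides how resistance from any earlier course is counted.

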4.3 Study Enrollment Procedures

[name] or study staff will consent and enroll potential participants from the pool of principal and co-investigators patients.

Recruitment will take place in Gonda 12 Otorhinolaryngology department during the patient's clinical visit.

There will be no screening log or other documentation of reasons of ineligibility.

The consent and enrollment process will occur in a private patient room on Gonda 12. When the consultant has completed discussing different treatment options with the patient, and the patient and the physician have decided on to pursue treatment with topical antibiotics, the study staff member will inform the patient that he/she meets the criteria for this study and describe the study to the patient. Total time of discussion is expected to be 10 minutes. The patient will be given adequate time to decide whether or not to participate in the study.

The patient will be informed by the study staff member of the possible risks and benefits of participation and study staff member will reinforce that this is a decision only the patient can ultimately make. The study staff member will also inform the patient that declining participation in the study will in no way affect the quality or duration of their care. Only patients who can consent for themselves will be enrolled in this study.

If the potential participant is a women age 18-50, the Mayo Clinic "Pre-Procedure Pregnancy Reasonably Excluded Guide (PREG)" will be administered. If pregnancy is reasonably excluded according to the guide, the patient will qualify for enrollment. If the patient is found to be pregnant, she will be excluded from the study.

5 STUDY INTERVENTIONS

5.1 Interventions, Administration, and Duration

The pre-intervention assessment will occur during the enrollment visit as part of routine clinical care. Once the results of the gram stain, culture and sensitivities are known, the patient will be prescribed the appropriate topical antibiotic for the study. They will be notified of the result of the gram stain, culture and sensitivities as well as their pending prescription via a phone call or other electronic means, as per study subject preference. The intervention will take over the course of 28 days as the patient uses the medication as an outpatient. There will be only one 28 day duration study intervention administered after the enrollment visit. There will be no modifications to this study intervention.

5.2 Handling of Study Interventions

After completion of the intervention, the patient will present for post-intervention assessment in the Department of Otorhinolaryngology on the 12th floor of the Gonda building in Rochester, MN with one of the staff rhinologists. This assessment will be exactly the same as the pre-intervention assessment. Specifically, this assessment will consist of 1) obtaining a nasal swab of mucopurulence from the affected sinus to be sent for gram stain, culture and sensitivity, 2) assessment of patient symptom severity score as measured by the self-administered Sino-Nasal Outcomes Test (SNOT-22) survey, and 3) assessment of patient physical exam as evaluated by rigid nasal endoscopy and documented in Lund-Kennedy endoscopic findings form.

5.3 Concomitant Interventions

5.3.1 Allowed Interventions

Any additional medications prescribed to the patient as part of their ongoing therapy for chronic rhinosinusitis including nasal saline irrigations, steroid irrigations, or topical sprays.

5.3.2 Required Interventions

None

5.3.3 Prohibited Interventions

Patients will be excluded if they are prescribed concomitant oral steroids

5.4 Adherence Assessment

Definition of adherence to study intervention will study subject attestation that they completed at least 48 / 56 dosages of nasal saline irrigation with topical antibiotic and presentation for one post-intervention assessment. Patient will record topical antibiotic use in a daily log. This log will be used by the investigators to assess adherence. These available endpoints will be taken and incorporated into analysis.

6 STUDY PROCEDURES

6.1 Schedule of Evaluations

Pre-Intervention assessment: to be completed before starting intervention

- Nasal swab: Obtain swab from affected sinus and send for gram stain, culture and sensitivity
- Patient symptom evaluation as assessed by SNOT-22 symptom scores
- Patient endoscopic physical exam as assessed by Lund-Kennedy endoscopic exam scores. Documentation photos will also be obtained with two endoscopic photos per side, one from the head of the inferior turbinate into the nasal cavity and one from the head of the middle turbinate towards the middle meatus.

Post-Intervention assessment: to occur after the completion of the 28 days of intervention with topical antibiotics

- Nasal swab: Obtain swab from affected sinus and send for gram stain, culture and sensitivity
- Patient symptom evaluation as assessed by SNOT-22 symptom scores
- Patient endoscopic physical exam as assessed by Lund-Kennedy endoscopic exam scores. Documentation photos will also be obtained with two endoscopic photos per side, one from the head of the inferior turbinate into the nasal cavity and one from the head of the middle turbinate towards the middle meatus.

6.2 Description of Evaluations

6.2.1 Screening Evaluation

Consenting Procedure

There will be a single informed consent form that describes both the screening and study procedures.

[name] MD or study staff will consent potential participants from the pool of principal investigator's and co-investigators' patients. When the staff member has completed discussing the intervention with the patient, the provider will inform the patient that he/she meets the criteria for this study. Total time of discussion is expected to be 10 minutes. The patient will be given time to decide if they would like to participate in the study.

Documentation of signed consent will be maintained through monitoring by [name] MD and study staff and/or ENT Committee. The documentation will be kept in a secure, locked cabinet in the Department of Otorhinolaryngology's Research office only accessible to PI and study staff.

Screening

Screening will be based on procedures that are part of standard patient care, and therefore, informed consent will not be obtained by study staff prior to screening

patients. Potential participants will come from the pool of patients diagnosed with chronic rhinosinusitis that the principal investigator and co-investigator consultants have treated.

Screening evaluation for patients in both groups includes:

- Patient Demographics
- Diagnosis of chronic rhinosinusitis
- Assessment of symptom score with SNOT-22 survey
- Physical Examination-Involves examination of the patients bilateral nasal cavities and paranasal sinuses with rigid endoscopy
- Pre-Procedure Pregnancy Reasonably Excluded Guide (PREG)

If the potential participant is a women age 18-50, the Mayo Clinic "Pre-Procedure Pregnancy Reasonably Excluded Guide (PREG)" will be administered. If pregnancy is reasonably excluded according to the guide, the patient will qualify for enrollment. If the patient is found to be pregnant, she will be excluded from the study.

The study staff will review these tests from the patient's medical records to determine eligibility. Time prior to enrollment within which the screening tests and evaluations must be performed is within 28 days of study enrollment.

6.2.2 Enrollment and Baseline

Enrollment

Enrollment will be defined as the date all screening criteria are met and individual agrees to participate. There will be a single informed consent form for both screening and study procedures. Enrollment and screening will be conducted during the same visit.

The criteria used for inclusion and exclusion will be collected from the patient on this date using the following tests:

- medication reconciliation
- Review of medical record

6.2.3 Post-treatment assessment

Post-treatment assessment must be performed after the completion of the intervention

7 SAFETY ASSESSMENTS

7.1 Specification of Safety Parameters

Safety will be assessed for administration of topical antibiotic via nasal irrigation that is the subject of the intervention under investigation. Assessment will include details of any adverse reaction at the site of irrigation.

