Our department has developed in conjunction with the infectious disease department and the Mayo pharmacy, an easy to implement set of topical antibiotics with easy to use capsules and set dosages for use by our patients. This is a pilot study designed with the hypothesis that topical antibiotics do not cause antibiotic resistance. In addition, data will be collected to investigate symptom and physical exam outcomes in patients undergoing topical antibiotic therapy as secondary outcomes. The study will be conducted on existing patients who would otherwise receive treatment with topical antibiotics as standard of care.

Moreover, many of patients who have recalcitrant chronic rhinosinusitis are infected by the bacteria pseudomonas aeruginosa. The use of the fluoroquinolone class of antibiotics is a treatment of choice for this pathogen. In 2008, the US Food and Drug Administration issued a "black box" advising manufacturers to warn providers and patients of risk increased risk of tendinitis, tendon rupture, peripheral neuropathy. A well-studied, viable alternative to oral fluoroquinolone that works well without the associated risks is warranted.

Finally, poor penetration of oral antibiotics to the sinonasal cavity due to the infection being within a space may limit the efficacy of oral antibiotics as a treatment. In contrast use of topical antibiotics in a patient who has previously undergone sinus surgery, provides a potentially more effective delivery of medication to the infected space⁸.

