2.2 Study Rationale

The interventional regimen is as follows.

Patient will undergo pre-intervention nasal swab from the affected sinus that will be sent for gram stain and bacterial culture and sensitivities.

If pathogen identified in the bacterial culture is pseudomonas aeruginosa, topical tobramycin or gentamycin will be assigned as first line agent pending culture profiles and cost factors. If the sensitivities show resistance to both tobramycin and gentamycin, then levofloxacin will be prescribed.

If the pathogen identified in the bacterial culture is other than pseudomonas aeruginosa, mupirocin will be prescribed. If the pathogen shows resistance to mupirocin, then the patient will be prescribed one of the other three antibiotics will be prescribed pending culture profiles and cost factors

The patient will use the topical antibiotic twice a day for 28 days. This will be accomplished by first proceeding with their normal nasal rinse regimen as prescribed by their physician (this may include saline alone, or saline with budesonide). Twice per day, at the end of each regimen, they perform one additional nasal saline rinse using the Neil Med sinus rinse bottle in the manner outlined on the packaging instructions. However, with this last additional nasal saline rinse, they will open their antibiotic capsule and drop the contents into the rinse bottle prior to rinsing.

Known and potential risks are as follows:

Potential risks of nasal saline irrigation is stinging sensation and burning Potential risks of filling the nasal saline irrigation rinse bottle with water that is too hot is mucosal burns

Potential risks of topical antibiotic administration include local pruritis and inflammation Potential risks of selection antibiotic resistant organisms. Potential risk for hearing loss

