7.2 Methods and Timing for Assessing, Recording, and Analyzing Safety Parameters

Assessment of adverse reaction at the post-intervention visit.

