7.3 Adverse Events and Serious Adverse Events

An **adverse event (AE)** is generally defined as any unfavorable and unintended diagnosis, symptom, sign (including an abnormal laboratory finding), syndrome or disease which either occurs during the study, having been absent at baseline, or if present at baseline, appears to worsen. Adverse events are to be recorded regardless of their relationship to the study intervention.

A serious adverse event (SAE) is generally defined as any untoward medical occurrence that results in death, is life threatening, requires inpatient hospitalization or prolongation of existing hospitalization, results in persistent or significant disability/incapacity, or is a congenital anomaly.

No serious adverse event out of character with nasal irrigations is expected.

Adverse events captured during interval clinical visit are captured as unsolicited events, but if patient reports by calling PI directly using number on the consent form it will be captured as a solicited event. The events will be recorded as such so that there are no double collection systems.

If there are any adverse events or serious adverse events reported by the patient to the co-investigators at any point post-interventional procedure throughout the study, the Principal Investigator will be notified within 24 hours.

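### Section 7 names only irrigation-site reactions and schedules no targeted enquiry about non-local effects; hearing loss has a planned summary but no scheduled measurement, and adverse events have no summary

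*Combined protocol and SAP*

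**What the plan says.** The safety plan is short. Section 7.1 says that the rinse is the object of safety assessment and gives one item of content: "Assessment will include details of any adverse reaction at the site of irrigation". The heading of 7.2 covers methods, timing, recording and analysis, but its text is one line: "Assessment of adverse reaction at the post-intervention visit".

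Section 7.3 is wider. An adverse event is "any unfavorable and unintended diagnosis, symptom, sign (including an abnormal laboratory finding), syndrome or disease", and "Adverse events are to be recorded regardless of their relationship to the study intervention". On labels, it treats events picked up at interval clinic visits as unsolicited. For telephone reports the rule differs: "if patient reports by calling PI directly using number on the consent form it will be captured as a solicited event".

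Two kinds of non-local harm appear elsewhere:

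- **Tendon and nerve effects.** Section 2.1 reports that manufacturers of fluoroquinolones were advised to "warn providers and patients of risk increased risk of tendinitis, tendon rupture, peripheral neuropathy". It uses this to argue for an alternative to the oral drug.
- **Hearing loss.** The risk list in 2.2 says "Potential risks of topical antibiotic administration include local pruritis and inflammation", then adds selection of resistant organisms and possible hearing loss. Tendon and nerve effects are not in that list.

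Levofloxacin is one of the four rinses. Under 2.2 it is a fallback: for Pseudomonas resistant to both aminoglycosides, or as one of three options when another pathogen resists mupirocin.

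The visit content in sections 3, 5.2 and 6.1 is swab, SNOT-22 and endoscopy, with photographs in 6.1. Section 9.5 plans a summary of audiometric data as its third secondary item and has no summary of adverse events.

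**The concern.** A broad definition of an adverse event settles what is written down once someone knows about it. It does not settle whether anyone asks. The only reaction that section 7 names is local, and the scheduled assessment has no question list. A patient may not connect numbness, tendon pain or a change in hearing with a nasal rinse, and may not mention it. If no such events appear in the results, a reader cannot tell whether none occurred or none were asked about.

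Three parts of the plan depend on this. The review triggers in 9.3 rest on counts of serious events, severe reactions and rising frequency, and so on events being detected. The audiometric summary in 9.5 needs data that no visit is scheduled to produce. And the solicited and unsolicited labels, which should tell a reader how an event was found, are assigned in a way that hides it.

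**Working it through.** The plan gives no safety rate or safety sample size, so there is no stated figure to reproduce. The check is a comparison of sections, with some small arithmetic.

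**1. What is named, sought and summarised.** Selection of resistant organisms is left out because it is the primary outcome and is measured by swab.

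| Effect | Where named | Scheduled enquiry or measurement | Planned summary in 9.5 |
|---|---|---|---|
| Local reaction | 2.2, 7.1 | Post visit (7.2), no questions given | None |
| Hearing loss | 2.2 | None in 3, 5.2, 6.1 or 7 | Audiometric mean (SD), median (range) |
| Tendon and nerve effects | 2.1, for the class, context of the oral drug | None | None |

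No row is complete. Hearing loss has a summary without a measurement. Local reactions have an assessment without a summary. Tendon and nerve effects have neither.

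**2. Timing.** The course is 28 days (2.2), and section 3 places the post visit within 21 days of completion. Counting from the first dose, the check falls between about day 28 and 28 + 21 = day 49. Section 6.2.3 alone sets no upper limit.

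**3. Levofloxacin exposure.** Section 3 gives 250 mg per rinse and 2.2 gives two rinses a day: 250 × 2 × 28 = 14,000 mg placed in rinses over a full course. This is not an absorbed dose, because the documents do not state systemic uptake. Nor do they estimate how many patients will receive levofloxacin.

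**4. Labels.** In ordinary use, a solicited event answers a question set in advance and an unsolicited event is volunteered. A call that the patient makes is volunteered, but 7.3 calls it solicited. Events at interval clinic visits are called unsolicited. That is right if the patient volunteers them and wrong if staff ask. Section 7.3 does not say which label applies to findings at the assessment in 7.2. If fixed questions were added and 7.3 left as it is, the answers could carry the wrong label.

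**5. Who is counted.** Section 8 allows replacement of participants who take fewer than 48 of 56 doses and says that those replaced are not counted. It also asks for safety data on anyone stopped because of an adverse event. With no adverse event table in 9.5, nothing ensures that those data are reported.

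**6. What asking could show at best.** Suppose every participant is asked about hearing and none reports a problem. With an exact two-sided 95% interval (an assumption, since 9.5 names no method), the upper limit is 1 − 0.025^(1/n). The documents give n as 20 (Précis and section 3) and as 40 (9.1 and 9.2):

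- n = 20: 1 − 0.025^(1/20) = 16.8%
- n = 40: 1 − 0.025^(1/40) = 8.8%

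For the subset given levofloxacin the limit would be higher. Asking makes a zero interpretable, but in a pilot of this size it does not show safety.

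**The case against.** The strongest reply is that the protocol's wording is broader than its one named parameter. Section 7.1 says what assessment will include, 7.2 is not restricted by body site, and 7.3 takes in any symptom whatever its cause. A reader might infer that safety assessment is confined to the nose. The text does not support that: a tendon or nerve event would be recorded if it became known. The gap is in ascertainment, not in the scope of recording.

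A reader might also infer that the plan ignores every non-local risk. That is too strong, because hearing loss is listed and an audiometric summary is planned. What remains is that the measurement is not scheduled.

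A third inference would be that the protocol accepts tendon and nerve harm as a risk of the rinse, or that the study sets out to show that this harm is avoided. Neither is stated. The warning is background on the oral drug, and avoiding class effects is neither an objective nor an outcome. What stands is that a study drug belongs to the class for which the protocol itself cites the warning, and no one is asked to enquire.

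Other replies have some force. Few patients may receive levofloxacin. Channels exist before the post visit: a telephone number, interval clinic visits and notification of the principal investigator within 24 hours. All of these wait for the patient to speak or attend. The consent pages are not in the text, so nothing can be said about what patients are told of class effects. Finally, questions at the post visit cannot find symptoms earlier in the course. That is correct, and the change below should not be presented as doing so.

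**Conclusion.** The point holds as a gap in targeted ascertainment and reporting of harms, and it should be corrected. It does not affect the primary resistance endpoint.

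Four things are established from the text alone: no scheduled enquiry about hearing, tendon or nerve effects; an audiometric summary with no scheduled measurement; a rule that labels a volunteered phone call as solicited; and no adverse event summary in 9.5.

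The size in missed events cannot be given. The documents state no event rate, no fraction of symptoms that patients would volunteer, no systemic uptake and no expected number on levofloxacin. The practical effect on tendon and nerve symptoms may be small because levofloxacin is a fallback. The hearing point is broader, since 2.2 lists that risk without tying it to one drug.

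The conclusion assumes that no separate case report form, outside these documents, already contains such questions. Section 10.1 names an enrolment form and a post-intervention form but does not give their content.

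**What to change.** - **7.1 and 7.2:** add fixed yes/no questions at the existing post-intervention visit on the non-local effects that the protocol itself names: hearing for all participants, and tendon and nerve symptoms for those given levofloxacin.
- **7.3:** label answers to these questions as solicited and spontaneous reports, including phone calls, as unsolicited.
- **9.5:** add an adverse event table by assigned drug, showing solicited and unsolicited events separately and including replaced participants.
- **Sections 2, 6, 7 and 9.5:** reconcile them on audiometry, so that any measurement summarised in 9.5 is scheduled at named visits and appears in section 7. Reconcile the warning in 2.1 with the risk list in 2.2, stating whether the sponsor regards it as relevant to the rinse.

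The questions, labels and table cost a few lines on an existing form, some rewording and one table, with no extra visit. The cost of audiometry depends on how the sponsor resolves that mismatch. The downside is that asking will bring in more non-specific symptoms and raise the reported count, and the levofloxacin row may hold few patients. The questions improve ascertainment at the post visit only. No change to any dose or treatment rule is proposed.
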